3.5.3.2 Construction of waterfall graphs

The waterfall graph is used to depict anti-tumor activity. This plot displays both BOR and the best percentage change from baseline in the sum of diameter of all target lesions for each patient.

The assessments with an unknown overall response will **not be** excluded as long as the sum of diameter is correctly computed on the same lesions assessed at baseline.

The best overall response will be shown above each of the displayed bars in the graph.

Patients will be ordered in the graph using the following display (from left to right):

- Bars above the horizontal axis representing tumor growth
- Bars under the horizontal axis representing tumor shrinkage

Waterfall plots will show the cut-off limits for target lesions for PD (+20%) and PR (-30%) as dotted lines.

On the top of the waterfall plot a heatmap will be added in order to display per patient (matching with the bar on the waterfall plot) the information regarding BRAF local mutational status.

3.5.3.3 Construction of swimmer plots

The plot will show duration of exposure (without display of dose interruption and dose change information), BOR status and on-going status or primary reasons for discontinuation by patient.

3.6 Safety evaluation

The assessment of safety is based on the type of AEs and frequency of AEs as well as on the number of laboratory values that fall outside of pre-determined ranges (Common Toxicity Criteria [CTC] version 4.03 grading limits or normal ranges as appropriate). Other safety data includes electrocardiogram, vital signs and Ocular.

The Safety set will be used for summaries and listings of all safety data in Section 14 of the CSR with the exception of dose limiting toxicities (DLT) for which the DDS will be used. Safety analyses will be performed per treatment received (see Section 2.1.1.2). The FAS will be used for Section 16 of the CSR, including for safety listings. These listings will be displayed per intended treatment as per all analyses performed on the FAS (see Section 2.2). Differences between treatment received and intended treatment, if any, will be provided in a listing.

The safety summary tables will include only assessments collected no later than 30 days after study treatment discontinuation. All safety assessments will be listed, and those collected later than 30 days after study treatment discontinuation will be flagged.

3.6.1 Adverse event

Adverse events are coded using the Medical Dictionary for Regulatory Activities (MedDRA, version 18.1) terminology. Although CTCAE version 4.03 grading is by definition a 5-point scale generally corresponding to mild, moderate, severe, life threatening and death, CTCAE grade 5 (death) will not be used since this information will be collected on the "End of Treatment", "Study evaluation completion" or "Survival information" CRF pages.

Separate summaries and listing for adverse events, serious AEs (SAEs) and death recorded during the study will be provided. Deaths will also be summarized by primary reason. Additional summaries and listings events suspected to be related to study drug by treatment, events leading to study drug discontinuation, and events requiring dose adjustment or delay will be produced.

Listing and summaries will be produced according to the following rules:

- Patients reporting and experiencing multiple occurrences of a specific AE will have occurrences listed but will be counted only once in the appropriate event category/class and according to the worst observed grade within summary tables.
- AEs will be summarized by one of the following methods: by presenting the number and percentage of patients having at least one AE, having at least one AE in each primary system organ class, and having at least one AE for each preferred term or by presenting the number and percentage of patients having at least one AE and having at least one AE for each preferred term. Within each type of summary, AEs will be sorted by descending frequency or alphabetically (system organ class [SOC] and preferred term [PT] or PT for summaries that do not include SOC information).
- Specific groupings of clinically notable adverse events will be considered and the number of patients with at least one event in each grouping will be reported. The case retrieval sheet for each of study drug (if available) will be used to identify risks of special interest. Adverse events of special interest (All and Grade 3/4) will be tabulated by groups of special interest and preferred term for each study drug separately. In addition, separate listing will be provided for each study drug.
- AEs with incidence thresholds of ≥20% in the summarized population will be tabulated by preferred term. Grade 3/4 AEs with incidence ≥5% will be summarized similarly. Treatment-related AEs with an incidence of ≥10% will be summarized distinctly for all AE grades and for Grade 3/4.

3.6.2 Dermatologic examination

All dermatological examination data will be listed.

3.6.3 Ophthalmic examination

All ophthalmic examinations (i.e., Tonometry, Visual acuity, Visual field, Fundoscopy, Slit lamp, Optical Coherence Tomography (OCT), Fluorescein Angiography (FA), Electroretinogram (ERG)) will be listed.

3.6.4 Laboratory data

All laboratory values will be converted into SI units when applicable and the severity grade calculated using the National Cancer Institutes Common Terminology Criteria for Adverse Events (CTCAE, version 4.03) unless otherwise indicated. A severity grade of 0 will be assigned when the value is within normal limits. In the case when a local laboratory normal range overlaps into the higher (i.e., non-zero) CTC grade, the laboratory value will still be considered within normal limits and assigned a CTC grade of zero.

The following summaries will be produced for the laboratory data by laboratory parameter:

- Shift tables to the worst post-baseline value from baseline value (both expressed in CTC grades) will be produced.
- Tables of worst post-baseline value by CTC grade.

• For laboratory parameters where CTC grades are not defined, shift tables to the worst post-baseline value will be produced using the low/normal/high classifications based on laboratory reference ranges.

The following listings will be produced for the laboratory data:

- Listing of patients with laboratory abnormalities of CTC grade 3 and 4 by parameter, cycle and treatment group
- Listing of laboratory normal ranges by laboratory identification number and laboratory group
- Listing of all laboratory data with values flagged to show corresponding CTC grades and/or the classifications relative to the laboratory reference ranges (i.e., High (H) or Low (L))

Table 3-2 lists all those laboratory parameters for which CTCAE grades are defined, Table 3-3 lists the remaining laboratory parameters.

3.6.4.1 Hematology

Differential counts will be converted to absolute values for CTC grade classification. For all the differential counts, % will be converted to absolute values, if necessary:

e.g. Absolute WBCdiff (Wunit) = Absolute WBC (Wunit)*Relative WBCdiff(%)/100

Normal ranges should not be converted to obtain absolute normal ranges. Absolute normal ranges should be provided within lab ranges. If both are reported, absolute values will be left unchanged. Grading will be applied to absolute values.

Hematology and coagulation						
		Biochemistry		Urinalysis		
	White Blood Cells (WBC)	↑↓	Creatinine	ſ	Urine Protein Dipstick test	1
	Hemoglobin	↑↓	Sodium (hyper & hypo)	$\uparrow \downarrow$		
	Platelets counts	Ļ	Potassium (hyper & hypo)	↑↓		
	Absolute Neutrophils	\downarrow	Glucose (hyper & hypo)	↑↓		
	Absolute Lymphocytes	↑↓	Magnesium (hyper & hypo)	↑↓		
	aPTT	1	Uric acid	↑		
	Fibrinogen	\downarrow	Albumin	\downarrow		
	INR	Î	AST (SGOT)	1		
			ALT (SGPT)	Ť		
			Alkaline Phosphatase	↑		
			Total Bilirubin	ſ		

Table 3-2Laboratory parameters to be presented in grade shift tables based on
CTC grade

Amylase	\uparrow
Lipase	↑
Total cholesterol	↑
Triglycerides	1
СРК	1
Phosphate (Inorganic Phosphorus)	\downarrow

↑ Indicates that CTC grade increases as the parameter increases, these parameters are to be included in the summary of maximum post-baseline lab parameters

 \downarrow Indicates that CTC grade increases as the parameter decreases, these parameters are to be included in the summary of minimum post-baseline lab parameters

Table 3-3	Laboratory parameters to be presented in shift tables based on local
	laboratory normal ranges

Hematology and coagulation	Biochemistry	Urinalysis
Red blood cell count (RBC)	Urea	Specific gravity
Absolute eosinophils	Total protein	Glucose
Absolute basophils	Indirect bilirubin	Blood
Absolute monocytes	Direct bilirubin	Bilirubin
Prothrombin time	HDL	Ketones
Hematocrit	LDH	Leukocytes
	Chloride	Myoglobin
	Bicarbonate	
	LDL	
	TSH	
	Free T3	
	Free T4	
	Total Calcium	

3.6.5 Vital signs, weight and physical examinations

All vital signs measures (e.g., oral temperature, respiratory rate, sitting blood pressure, and sitting pulse) and weight will be listed by parameter, treatment group, patient and time point (cycle) for each patient with at least one notable vital sign abnormality on record. Vital sign abnormalities as defined in Table 3-4 will be derived and displayed in the listings.

The number and percentage of patients with at least one post-baseline vital sign abnormality (in both directions, i.e., both clinically notable high and low values) will be tabulated.

Table 3-4	Notable vital signs ranges
-----------	----------------------------

Vital sign	Criteria for clinically notable ranges
Systolic blood pressure	≥180 mmHg/≤90 mmHg with increase/decrease from baseline of ≥20

Pfizer Inc.

[mmHg]	mmHg
Diastolic blood pressure [mmHg]	≥105 mmHg/≤50 mmHg with increase/decrease from baseline of ≥15 mmHg
Pulse rate [bpm]	≥120 bpm/≤50 bpm with increase/decrease from baseline of ≥15 bpm
Oral body Temperature [°C]	Body temperature: \leq 35, \geq 39
Weight [kg]	≥10% decrease/increase from baseline

3.6.6 WHO/ECOG performance status

Frequencies and percentages for the categories of the WHO performance scale will be summarized by visit.

3.6.7 Electrocardiograms

3.6.7.1 ECG data descriptive statistics

• Data from electrocardiogram will be listed, notable values will be flagged, and any other information collected will be listed. The frequency and percentage of patients with newly occurring qualitative ECG abnormalities will be tabulated. Shift table baseline to worst on-treatment result for overall assessments will also be summarized.

• Post-baseline values will also be categorized and tabulated to flag notable values according to the following rules:

Parameters	Criteria for ECG notable values	
QTcF (ms), QTcB (ms) and QT (ms)	New: > 450, > 480, > 500 ms	
	Increase from baseline > 30	
	Increase from baseline > 60	
HR (bpm)	Increase from baseline > 25% & to a value > 100	
	Decrease from baseline < 25% & to a value < 50	
PR (ms)	Increase > 25% to a value > 200	
QRS (ms)	Increase > 25% to a value > 110	

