Table 14.3.1.3.3d	Treatment-emergent adverse events	Safety Set	Phase Ib/II, Triple
14016 14.3.1.3.30	(treatment related) occurring in >=	Salety Set	Combination
	10% of patients by preferred term,		Combination
	maximum grade and treatment		
	5		
T. I.I. 442224	group/arm		
Table 14.3.2.2.1a	Deaths, by preferred term and	Safety Set	Phase Ib, Dual
	treatment group		Combination
Table 14.3.2.2.1b	Deaths, by preferred term and arm	Safety Set	Phase II, Dual
			Combination
Table 14.3.2.2.1d	Deaths, by preferred term and	Safety Set	Phase Ib/II, Triple
	treatment group/arm		Combination
14.3.2.2.2a	Deaths, by primary reason and	Safety Set	Phase Ib, Dual
	treatment group		Combination
14.3.2.2.2b	Deaths, by primary reason and arm	Safety Set	Phase II, Dual
			Combination
14.3.2.2.2d	Deaths, by primary reason and	Safety Set	Phase Ib/II, Triple
	treatment group/arm		Combination
Table 14.3.4.1.1d	Hematology and coagulation shift	Safety Set	Phase Ib/II, Triple
	table based on CTC grade by	,	Combination
	parameter and treatment group/arm		
Table 14.3.4.1.2d	Hematology and coagulation shift	Safety Set	Phase Ib/II, Triple
	table based on normal range by		Combination
	parameter and treatment group/arm		
Table 14.3.4.1.3d	Biochemistry shift table based on CTC	Safety Set	Phase Ib/II, Triple
10016 14.3.4.1.30	grade by parameter and treatment	Jarely Jel	Combination
	group/arm		Combination
Table 14 2 4 1 4 -		Cofoty Cot	Dhacath/IL Triala
Table 14.3.4.1.4d	Biochemistry shift table based on	Safety Set	Phase Ib/II, Triple
	normal range by parameter and		Combination
T 440 + 45	treatment group/arm		
Table 14.3.4.1.5d	Urinary shift table based on CTC	Safety Set	Phase Ib/II, Triple

	grade by parameter and treatment group/arm		Combination
Table 14.3.4.1.6d	Urinary laboratory parameters without CTC grades by visit and treatment group/arm	Safety Set	Phase Ib/II, Triple Combination
Table 14.3.4.1.7d	Notable hepatic laboratory values by parameter and treatment group/arm	Safety Set	Phase Ib/II, Triple Combination
Table 14.3.5.2d	Notably abnormal vital signs by treatment group/arm	Safety Set	Phase Ib/II, Triple Combination
Table 14.3.6.2.1d	Notable ECG values per central analysis by treatment group/arm	Safety Set	Phase Ib/II, Triple Combination
Table 14.3.6.2.2d	New clinically meaningful ECG abnormalities per central analysis, by evaluation type and treatment group/arm	Safety Set	Phase Ib/II, Triple Combination

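### The low heart-rate criterion for notable ECG values has its inequality reversed, so Table 14.3.6.2.1d would count small falls below 50 bpm and omit the large ones

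*SAP*

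**What the plan says.** SAP Section 3.6.7.1 introduces the ECG criteria with "Post-baseline values will also be categorized and tabulated to flag notable values according to the following rules". The percentage criteria in the table that follows are:

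- Heart rate, high: "Increase from baseline > 25% & to a value > 100"
- Heart rate, low: "Decrease from baseline < 25% & to a value < 50"
- PR: "Increase > 25% to a value > 200"
- QRS: "Increase > 25% to a value > 110"

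The output that plainly depends on them in the final CSR is Table 14.3.6.2.1d, titled "Notable ECG values per central analysis by treatment group/arm" (Section 4.1.1; Safety Set, triple combination).

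Table 3-4 in Section 3.6.5 has a separate criterion for pulse rate as a vital sign: "≥120 bpm/≤50 bpm with increase/decrease from baseline of ≥15 bpm". Nothing else in the SAP corrects or explains the sign in the low heart-rate row.

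**The concern.** A notable-value criterion of this kind has two parts: the value is beyond a limit, and it has moved far enough from the patient's own baseline to suggest an effect of treatment. The second part is there to exclude people whose value was always close to the limit. The low heart-rate row does the opposite. It keeps patients who moved little and drops those who moved a lot.

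At stake is a safety summary for a three-drug combination. If the row is programmed as printed, its low heart-rate line would report patients with naturally slow rates and leave out marked on-treatment falls. A reader of the table could not tell that this had happened.

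**Working it through.** The SAP gives no figure to reproduce here, so the check is one of logic, using the criteria in Section 3.6.7.1 and the pulse criterion in Table 3-4.

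**Notation.** Let b be the baseline rate and v the post-baseline rate, in bpm, with v < b. The percentage fall is 100 × (b − v)/b.

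- Printed rule: (b − v)/b < 0.25 and v < 50.
- Rule in the same direction as the other rows: (b − v)/b > 0.25 and v < 50.
- Table 3-4 pulse rule, low side: v ≤ 50 and b − v ≥ 15.

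**Which baselines can be flagged as printed.** (b − v)/b < 0.25 is the same as v > 0.75b. With v < 50 this gives 0.75b < 50, so b < 50/0.75 = 66.7 bpm. In whole bpm the highest qualifying value is 49, and 49/0.75 = 65.3, so the highest baseline that can ever be flagged is 65.

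**Examples.** The last column assumes that the vital-signs pulse shows the same values as the ECG.

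| Baseline to value (bpm) | Fall | Printed rule | Rule with > 25% | Table 3-4 pulse rule |
|---|---|---|---|---|
| 80 to 45 | 35/80 = 43.8% | no | yes | yes (fall of 35) |
| 70 to 48 | 22/70 = 31.4% | no | yes | yes (fall of 22) |
| 60 to 44 | 16/60 = 26.7% | no | yes | yes (fall of 16) |
| 52 to 38 | 14/52 = 26.9% | no | yes | no (fall of 14) |
| 60 to 46 | 14/60 = 23.3% | yes | no | no (fall of 14) |
| 55 to 49 | 6/55 = 10.9% | yes | no | no (fall of 6) |
| 52 to 49 | 3/52 = 5.8% | yes | no | no (fall of 3) |

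**Overlap.** Take every whole-bpm pair with baseline 50 to 110 and post-baseline value 30 to 49: 61 × 20 = 1220 pairs. The printed rule flags 100, the rule with > 25% flags 1116, and no pair is flagged by both. The remaining 1220 − 100 − 1116 = 4 pairs are falls of exactly 25% (52 to 39, 56 to 42, 60 to 45, 64 to 48), which neither rule flags. These are counts of possible value pairs, not expected numbers of patients. They show that the two rules select entirely different cases.

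**Is it a slip or a choice?** The three other percentage criteria in the table each set a minimum change, and so does the pulse criterion in Table 3-4, in both directions. The low heart-rate row is the only one that sets a maximum.

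**The case against.** The strongest reply is that this is a visible slip with limited reach. Its parts deserve separate answers.

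- **A programmer would read it correctly.** The row may have been meant as a signed change below −25%, and anyone comparing it with its neighbours would probably query it. That lowers the risk but does not remove it: the row speaks of a decrease, so the printed sign is wrong on either reading, and independent programming from the SAP could reproduce the error. The Introduction allows obvious minor formatting and spelling mistakes to be corrected without an amendment. That does not clearly cover a change in who is counted.
- **The pulse table would catch these patients.** This largely stands. If the pulse matched the ECG, the Table 3-4 rule would flag 80 to 45 and 70 to 48, and Table 14.3.5.2d reports notable vital signs for the same triple-combination Safety Set. From a baseline of 60 bpm upward, any fall of more than 25% exceeds 0.25 × 60 = 15 bpm and so meets the change requirement. But pulse is a different measurement, some falls from lower baselines escape both rules (52 to 38), and a correct pulse table does not make the ECG table right. A reader might infer that low heart rates would vanish from the safety report altogether; the SAP does not support that.
- **The reach is one table.** A reader might infer that shift table 14.3.6.2.3d is wrong too. Its title refers to notable values, but Section 3.6.7.1 describes a shift in the overall assessment, and a criterion based on change from baseline cannot by itself classify a baseline value. Dependence is possible, not established. A reader might also infer that flags in the final CSR listings would be wrong. Section 3.6.7.1 does plan a flagged ECG listing, but the Introduction limits the final analysis to the Section 4 appendices, and Section 4.1.2 contains no ECG listing. So there are no such flags in that report, and equally no listing from which missed patients could be found.

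**Conclusion.** The criterion is wrong as written. Applied literally, it can flag only patients with a baseline below 66.7 bpm, and only for falls of less than 25% that end below 50 bpm. It misses every larger fall to below 50 bpm. The low heart-rate counts in Table 14.3.6.2.1d would then be wrong, and the final CSR plans no ECG listing to set them right.

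This rests on two assumptions: that the program follows the printed text, and that the intended rule is the one consistent with the rest of the table. The SAP does not show the program, so it would be too strong to say that any output, interim or final, has been misreported. It would also be too strong to treat this as a threat to the trial's main conclusions. The ECG criteria are descriptive and feed no response, DLT or MTD analysis, and the QT, PR, QRS and high heart-rate criteria are unaffected. It is a moderate correction to safety reporting.

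**What to change.** In the ECG table of Section 3.6.7.1, reverse the inequality in the low heart-rate row so that it requires a decrease from baseline of more than 25%, to a value below 50 bpm, in line with the high heart-rate, PR and QRS rows.

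Then check the program behind Table 14.3.6.2.1d, and that behind 14.3.6.2.3d if it uses this row. Check also whether any output for the interim CSR used the printed rule, and correct it if so. Record the change in the SAP's change-control table rather than making it silently.

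The cost is one character in the SAP, a program check and, if the printed rule was coded, a re-run of the affected ECG tables. No new data are needed.

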3.6.7.2 PK/QT analyses

Not applicable.

3.6.8 Other safety analyses

Cardiac imaging with decreased left ventricular ejection fraction (LVEF) will be summarized based on worst CTC grade and listed.

Any other safety information collected will be listed and notable values will be flagged.

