An initial interim CSR will be prepared based on all Phase Ib/Phase II patient data from the dual study drug combination. The cut-off for reporting will be either LPFV + 18 months or when 80% of the patients can be assessed for progression free survival (PFS), whichever occurs first. Additional data for patients continuing to receive the MEK162 and LGX818 dual combination beyond the cutoff point for the initial reporting, as allowed by the protocol, and the Phase Ib/II data from the LGX818 and MEK162 and LEE011 triple combination will be summarized in a final CSR once all patients have discontinued the study. Although this SAP provides comprehensive detail on analyses performed throughout the lifetime of the study, only analyses included in the appendices for the final CSR (Section 4: Final Analysis Appendices) will be performed for the final analysis. For the presentation of results in the final analysis, LGX818, MEK162, and LEE011 will be referred to by their respective generic names: encorafenib, binimetinib, and ribociclib.

In this document, the dual and triple combination refers to the combination of LGX818 and MEK162, and LGX818 and MEK162 and LEE011, respectively, when not specified.

The purpose of the CSRs is to report the estimated maximum tolerated dose (MTD) and/or recommended phase II dose (RP2D), characterize the dose limiting toxicities (DLT), safety profile and efficacy of LGX818/MEK162 and LGX818/MEK162/LEE011 combinations in patients with solid tumors harboring a BRAF V600 mutation.

In addition, the CSR also report the assessment of clinical efficacy and safety of the LGX818 and MEK162 combination in patients with BRAF V600 mutant metastatic colorectal cancer (mCRC), patient with BRAF V600 mutant metastatic melanoma, who have progressed after prior selective BRAF inhibitor and patient with BRAF V600 mutant metastatic melanoma, who are naïve to prior selective BRAF inhibitor treatment.

[figure not shown]
An interim analysis is planned for the phase II part of patients with BRAF V600 mutant mCRC, when 50% of the total sample size (14 patients) have completed four cycles of treatment, to allow stopping early for futility when there is no treatment effect.

[figure not shown]
Note that obvious corrections will be made at the time of analysis to address minor formatting or spelling mistakes present in the SAP without the need to amend this document.

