1.5 CSR related reporting events

The following points will guide the production of all or subset of the planned analyses:

- The initial interim CSR (refened to as the initial CSR in protocol) includes all outputs described for the dual combination, with the data cut-off of August 31, 2015. This SAP describes the analysis for the initial interim CSR.
- The final CSR includes all outputs described for the triple combination and listing for the dual combination, with the data cut-off on or after all patients have completed or discontinued from the study.
- CCI

2 Definitions and general methodology

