Table 14.3.6.2.3d	ECG shift table based on notable values by treatment group/arm	Safety Set	Phase Ib/II, Triple Combination
Table 14.3.7.1d	Left ventricular ejection fraction worst CTC grade by treatment group/arm	Safety Set	Phase Ib/II, Triple Combination
Table 14.3.8.1d	WHO/ECOG performance status by treatment group/arm	Safety Set	Phase Ib/II, Triple Combination
Table 14.4.1.1a	Duration of exposure to study drug by treatment group	Safety Set	Phase lb, Dual Combination
Table 14.4.1.1b	Duration of exposure to study drug by arm	Safety Set	Phase II, Dual Combination
Table 14.4.1.1d	Duration of exposure to study drug by treatment group/arm	Safety Set	Phase Ib/II, Triple Combination
Table 14.4.1.2d	Dose reductions of study treatment by treatment group/arm	Safety Set	Phase Ib/II, Triple Combination
Table 14.4.1.3d	Dose delays of study treatment by treatment group/arm	Safety Set	Phase Ib/II, Triple Combination
Table 14.4.1.4a	Summary statistics of exposure of study treatment by treatment group	Safety Set	Phase Ib, Dual Combination
Table 14.4.1.4b	Summary statistics of exposure of study treatment by arm	Safety Set	Phase II, Dual Combination
Table 14.4.1.4c	Summary statistics of exposure of study treatment by treatment group/arm	Safety Set	Phase Ib/II, Dual Combination
Table 14.4.1.4d	Summary statistics of exposure of study treatment by treatment group/arm	Safety Set	Phase Ib/II, Triple Combination
Table 14.4.2.1d	Concomitant medications and significant non-drug therapies started prior to the start of study drug by	Safety Set	Phase Ib/II, Triple Combination

	preferred term and treatment group/arm		
Table 14.4.2.2d	Concomitant medications and significant non-drug therapies started after the start of study drug by preferred term and treatment group/arm	Safety Set	Phase Ib/II, Triple Combination
Table 14.4.2.3a	Antineoplastic therapy since discontinuation of study drug by preferred term and treatment group	Safety Set	Phase lb, Dual Combination
Table 14.4.2.3b	Antineoplastic therapy since discontinuation of study drug by preferred term and arm	Safety Set	Phase II, Dual Combination
Table 14.4.2.3d	Antineoplastic therapy since discontinuation of study drug by preferred term and treatment group/arm	Safety Set	Phase Ib/II, Triple Combination
Table 14.4.4.1.1	Summary of encorafenib concentrations by treatment group	Full Analysis Set	Phase Ib
Table 14.4.4.1.2	Summary of encorafenib concentrations by arm	Full Analysis Set	Phase II

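### Section 4 provides no output for dual-combination LVEF, ECG or vital-sign data after 31 August 2015, and no dual laboratory or SAE table, contrary to Sections 1, 1.5 and 3.6

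*SAP*

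**What the plan says.** Four parts of the SAP determine what the final CSR will report on dual-combination safety.

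- **Section 1 (Introduction).** The data to be summarised in the final CSR include "Additional data for patients continuing to receive the MEK162 and LGX818 dual combination beyond the cutoff point for the initial reporting". The same paragraph limits the work: "only analyses included in the appendices for the final CSR (Section 4: Final Analysis Appendices) will be performed for the final analysis".
- **Section 1.5.** The interim CSR holds all dual outputs, "with the data cut-off of August 31, 2015". For the later report, "The final CSR includes all outputs described for the triple combination and listing for the dual combination".
- **Sections 3.6 to 3.6.8.** Section 3.6 says all safety assessments will be listed. Section 3.6.8 adds "Cardiac imaging with decreased left ventricular ejection fraction (LVEF) will be summarized based on worst CTC grade and listed". Section 3.6.7.1 adds "Data from electrocardiogram will be listed, notable values will be flagged, and any other information collected will be listed". Section 3.6.5 promises a table of patients with notable vital signs and a listing for those patients. Section 3.6.4 promises laboratory shift tables, and Section 3.6.1 a separate SAE summary. None of these is limited to one combination.
- **Section 4.** The LVEF table, "Left ventricular ejection fraction worst CTC grade by treatment group/arm", is number 14.3.7.1d, with the subset given as Phase Ib/II, Triple Combination. The ECG, vital-sign, laboratory and SAE tables carry the same suffix and subset.

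**The concern.** Because Section 1 makes Section 4 the only source of final-CSR outputs, an output missing from Section 4 will not be produced under this plan. Dual patients who stayed on treatment past August 2015 may have later LVEF, ECG, vital-sign and laboratory results. The SAP says these will be summarised (Section 1) or at least listed (Sections 1.5 and 3.6).

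The planned summaries for LVEF and laboratory data use the worst post-baseline grade, and the ECG shift table uses the worst on-treatment result. For a given patient, a worst value can only stay the same or worsen as on-treatment follow-up lengthens. Dual tables frozen at the interim cut-off are therefore a lower bound that the final CSR would not update. The same CSR does update dual exposure, PFS, OS and DOR, so measured safety and those outcomes would rest on different cut-offs.

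**Working it through.** The plan gives no figure to reproduce. The check compares the methods text with the Section 4 output lists by table suffix and subset (a = Phase Ib dual, b = Phase II dual, c = Phase Ib/II dual, d = triple).

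| Domain | Methods text | Triple tables in 4.1.1 | Dual tables in 4.1.1 | Listing in 4.1.2 |
|---|---|---|---|---|
| LVEF | 3.6.8: summarise and list | 1 (14.3.7.1d) | 0 | none |
| ECG | 3.6.7.1: tabulate and list | 3 (14.3.6.2.1d to 3d) | 0 | none |
| Vital signs | 3.6.5: tabulate; list patients with a notable value | 1 (14.3.5.2d) | 0 | none |
| Laboratory | 3.6.4: shift tables and listings | 7 (14.3.4.1.1d to 7d) | 0 | 12 (16.2.8.1.1 to 12), no subset limit |
| SAE | 3.6.1: separate summary and listing | 1 (14.3.1.2.3d) | 0 | none separate; within AE listing 16.2.7.1 |

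Total for the five domains: triple 1 + 3 + 1 + 7 + 1 = 13; dual 0.

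**All tables numbered 14.3.**
- Triple: 1 DLT + 10 AE (including SAE) + 2 deaths + 7 laboratory + 1 vital signs + 3 ECG + 1 LVEF + 1 performance status = 26.
- Dual: 6 AE table types × 2 (a and b) = 12, plus 2 deaths table types × 2 = 4, giving 16. All 16 are AE or deaths tables.

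**What remains for dual patients.**
- AE tables: all treatment-emergent AEs by preferred term with grade 3/4 (14.3.1.2.2a/b), AEs leading to discontinuation (4a/b), AEs in at least 20% of patients (6a/b), grade 3/4 AEs in at least 5% (7a/b), and treatment-related AEs (14.3.1.3.2a/b and 3a/b).
- Deaths tables: 14.3.2.2.1a/b and 14.3.2.2.2a/b.
- Listings: AE listing 16.2.7.1 and the twelve listings under 16.2.8.1 show no subset. Section 4.1.2 marks triple-only listings explicitly (for example 16.2.7.2), so these are read as covering dual patients.
- Exposure and efficacy: 14.4.1.1a/b, 14.4.1.4a/b/c, OS 14.2.2.1b, PFS 14.2.3.1b and DOR 14.2.5.1b.

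**Statements against outputs.** Under Section 1 (summarised), the five domains fail for dual patients because they have no table of their own. Under Section 1.5 (listed), LVEF, ECG and vital signs fail because no such listing exists. Section 3.6 (all safety assessments listed) fails for the same three domains, in both combinations. Section 4 also does not follow Section 1.5 in the other direction, since it plans many dual tables and not only listings. None of the three statements describes what Section 4 contains.

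**The case against.** The strongest reply is that the reduced dual package is deliberate. Section 1 says the SAP covers analyses over the life of the study and that only Section 4 is run at the end. Section 1.5 assigns the full dual outputs to the interim CSR and a listing to the final one. On that reading, the summaries in Sections 3.6.5, 3.6.7.1 and 3.6.8 were owed to the interim report. Much of this stands: the mismatch between methods text and Section 4 would not be a defect by itself, and the omission of some dual tables looks at least partly intended. It does not explain the three missing listings, or the conflict between Sections 1 and 1.5, and the SAP gives no reason for leaving these domains out.

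Three stronger readings are tempting, and the SAP does not support them.

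- A reader might infer that late organ toxicity in dual patients goes unsummarised altogether. It does not: toxicity reported as an AE is tabulated by preferred term and grade 3/4, as are AE discontinuations and deaths, and laboratory values are listed.
- A reader might infer that dual efficacy is fully updated while safety is cut. Dual efficacy is also reduced: the best-overall-response and time-to-response tables (14.2.1.1d and 14.2.4.1d) are triple only, and Section 3.5.1.2 says post-treatment progression and survival follow-up stopped for Phase II from amendment 10.
- A reader might infer that only dual patients lose listings. The LVEF, ECG and vital-sign listings are missing for triple patients too.

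**Conclusion.** The point holds in a limited form. Sections 1, 1.5 and 3.6 disagree with Section 4. As written, any dual LVEF, ECG or vital-sign values collected after 31 August 2015 reach no final-CSR output, and dual laboratory grade shifts and SAEs have no table of their own. The size in outputs is 13 triple tables against 0 dual in these five domains, plus three listings absent for everyone.

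The size in patients cannot be stated. The SAP does not give the number of dual patients treated after the cut-off, their exposure, or how often these assessments continued. A reader might infer about seven years of unreported exposure, since the interim cut-off precedes the final-analysis revision of 20 September 2022 by 7 years and 20 days. That is a calendar span to a draft date. It is not patient exposure, and the final cut-off date is not given.

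The conclusion assumes that at least some dual patients had such assessments after the cut-off, and that Section 4 is applied as the exclusive list Section 1 says it is.

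**What to change.** 1. In Section 4.1.2, add LVEF, ECG and vital-sign listings covering both combinations, as Sections 3.6, 3.6.5, 3.6.7.1 and 3.6.8 require.
2. In Section 4.1.1, add dual versions (suffixes a and b, Safety Set, cumulative to the final cut-off) of the SAE table (14.3.1.2.3), LVEF worst grade (14.3.7.1), notable ECG values (14.3.6.2.1), notable vital signs (14.3.5.2) and the three laboratory CTC shift tables (14.3.4.1.1, 14.3.4.1.3 and 14.3.4.1.5). That is 7 table types × 2 = 14 tables.
3. Align Sections 1 and 1.5 with Section 4, so that all three state the same dual content for the final CSR. If any of these dual tables is still left out on purpose, say so and give the reason.

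The triple versions are already specified, so the tables are re-runs on another subset. The three listings need new shells. The change calls for no additional data collection. The cost is some extra programming, checking and CSR pages, and some tables may be sparse if few dual patients continued.
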